### **B. Severity, relationship of event to study drug or vaccine and outcome**

The severity of a clinical adverse event is to be scored according to the following scale:

- (1) Mild: Awareness of sign or symptom, but easily tolerated.
- (2) Moderate: Discomfort enough to cause interference with usual activity
- (3) Severe: Incapacitating with inability to work or perform usual activity.
- (4) Life-threatening: Patient at risk of death at the time of the event.
- (5) Death.

### **C. Assessment of Causality**

The relationship between the study vaccines and drugs and the occurrence of each SAE will be determined by the project physician in consultation with the site PIs based on their clinical judgment. Alternative causes, such as the natural history of the underlying diseases, concomitant therapy, other risk factors, and the temporal relationship of the event to the study drug will be considered and investigated. The site PIs will consult the lead PIs and the DSMB if this is deemed to be necessary.

There may be situations where the PIs have very minimal information about a SAE to include in the initial report. However, every attempt will be made to make an assessment of causality for every SAE prior to reporting to the IDMC. The PIs may change their opinion of causality in light of follow-up information, and may amend the SAE case report form accordingly.

The relationship of an adverse event to study vaccine or drug will be assessed according to the following definitions:

- (1) Definitely unrelated: events that had occurred prior to administration of the study drugs or events that are obviously unrelated to the study (e.g. accidental injury).
- (2) Unlikely: There is no reasonable temporal association between the study drug and the suspected event and the event could have been produced by the child's clinical state or other concomitant medications.
- (3) Possible: The suspected adverse event may or may not have a reasonable temporal association with the administration of study drug but the nature of the event is such that an association with the study drug cannot be ruled out. The event could be related to the child's clinical state or by concomitant medications.
- (4) Probable: The suspected adverse event follows a reasonable temporal sequence after administration of study drugs, abates upon discontinuation of the drug, and cannot be reasonably explained by the known clinical state of the child.
- (5) Definitely related: events that have no uncertainty in their association to the administration of study drugs.

The outcome of each AE must be assessed according to the following classification:

|                                   |  |
|-----------------------------------|--|
| 1) Completely recovered :         | The child has fully recovered with no observable residual effects.       |
| 2) Not yet completely recovered : | The child's condition has improved, but still has some residual effects. |
| 3) Deterioration :                | The child's overall condition has worsened                               |
| 4) Permanent damage :             | The AE has resulted in a permanent impairment                            |
| 5) Death :                        | The child died due to the AE.  |
| 6) Ongoing :                      | The AE remains the same as at onset.                                     |
| 7) Unknown :                      | The outcome of the AE is not known because of lost to follow-up          |

#### D. Reporting of adverse events and SAEs

All serious adverse events will be reported using a SAE report form which will have a detailed narrative of the events including information on the date the event started, severity, possible relationship to study drugs, concomitant medications, action taken, and outcome of the event.

A list of all SAEs will be compiled monthly or three monthly as requested by the DSMB and provided to the DSMB and GSK. Any SAE potentially related to the vaccine or drug administration will be reported to the DSMB and institutional Ethics Committees within 72 hour.

SAEs will be reported promptly to GSK within the timeframes described in Table A, once the investigator determines that the event meets the protocol definition of a SAE.

Table B. Timeframes for submitting serious adverse event and other events reports to GSK Biologicals

| Type of Event              | Initial Reports |  | Follow-up of Relevant Information on a Previous Report |  |
|----------------------------|-----------------|--|--|--|
|                            | Timeframe       | Documents                                  | Timeframe  | Documents                                  |
| SAEs                       | 72 hours*‡      | electronic Expedited Adverse Events Report | 72 hours***  | electronic Expedited Adverse Events Report |
| AEs of specific interest** | 72 hours*‡      | electronic Expedited Adverse Events Report | 72 hours***  | electronic Expedited Adverse Events Report |

\* Timeframe allowed after receipt or awareness of the information.

\*\* AEs of specific interest include meningitis and pIMDs.

\*\*\* Within receipt of information on the outcome of the SAE

‡ The investigator will be required to confirm review of the SAE/AEs of specific interest causality by ticking the 'reviewed' box in the GSK electronic Expedited Adverse Events Report within 72 hours of submission of the SAE/AEs of specific interest.

#### Reporting events of special interest

AEs of specific interest (pIMDs, and meningitis occurring within 30 or 42 days of vaccination) will be reported promptly to GSK within the timeframes described in Table B, once the investigator determines that the event meets the protocol definition of an AEs of specific interest (pIMDs and meningitis within 30 or 42 days of vaccination).

Contact information for reporting serious adverse events and AEs of specific interest

| Study Contact for Reporting SAEs and AEs of specific interest*  |
|--|
| Refer to the local study contact information document.   |
| Back-up Study Contact for Reporting SAEs and AEs of specific interest*  |
| 24/24 hour and 7/7 day availability:   |
| GSK Biologicals Clinical Safety & Pharmacovigilance
Outside US & Canada sites:
[contact] or [contact]
Email address: [contact] |

## Appendix 3

## Summary Study Information

### Study title

Seasonal vaccination with the RTS,S/AS01E malaria vaccine given with or without seasonal malaria chemoprevention: extension of a randomised, double-blind Phase 3 trial until children reach the age of five years.

### Clinical trial registration

Clinicaltrials.gov Identifier: [NCT04319380](https://clinicaltrials.gov/ct2/show/NCT04319380)

This study is an extension of an earlier clinical trial, [NCT03143218](https://clinicaltrials.gov/ct2/show/NCT03143218): 'A comparative trial of seasonal vaccination with the malaria vaccine RTS,S/AS01E, seasonal malaria chemoprevention, and of the two interventions combined.'

### Study duration

Original trial: April 2017 – March 2020;  
Extension Study: April 2020 – March 2022.

### Study site

The study is being conducted in Houndé district, Burkina Faso and in Bougouni district, Mali.

### Study objectives

#### Original Trial

The original trial sought to determine

1. Whether seasonal vaccination with RTS,S/AS01E was non-inferior to four monthly courses of seasonal malaria chemoprevention (SMC) with sulphadoxine-pyrimethamine plus amodiaquine (SP+AQ) in preventing clinical malaria and other adverse outcomes.
2. Whether the combination of these two interventions (i.e. seasonal vaccination with RTS,S/AS01E and SMC with SP+AQ) was superior to RTS,S/AS01E alone or SMC alone in preventing clinical malaria and other adverse outcomes.

These aspects were considered to be of equal priority.

#### Extension Study

The extension study, undertaken in children aged three or four years old who had previously received five doses of the RTS,S/AS01E malaria vaccine or comparator vaccines, together with seasonal malaria chemoprevention (SMC) with sulphadoxine-pyrimethamine (SP) plus amodiaquine (AQ) or placebo set out to determine whether :

1. Vaccination with a booster dose of the RTS,S/AS01E malaria vaccine at the beginning of the malaria transmission until children reach the age of five years is non-inferior to SMC in preventing clinical attacks of malaria and would be easier to deliver than SMC.

2. Administration of further doses of RTS,S/AS01 E at the beginning of the malaria transmission until children reach the age of five years provides additional protection against clinical episodes of malaria when given together with SMC.

A key question for policy makers and malaria control programme managers is the impact of the two interventions and their combination in the first five years of life (the age range for which seasonal malaria chemoprevention is the current standard of care in most countries where it is policy). The primary focus of the overall study is, therefore, determination of the impact of the two interventions and their combination over the whole five-year period (the three-year initial study, plus the two-year extension), and its interpretation will, therefore, be based on the cumulative incidence of malaria until children reach the age of five years, and are no longer eligible for SMC.

The primary objective of the extension study is determination of potential added value of extending administration of the two interventions and their combination beyond the age of three years. This will be based on the results obtained in the final two years of the study, based on the objectives described above.

## Study groups

This is a double-blind, individually-randomised trial with three study arms. For reference, the interventions given during the initial three-year trial are shown first, with the interventions given during the extension study shown separately.

### Group 1 – SMC arm - 'SMC alone'

Original Trial:

In 2017, children in the SMC group were given three doses of rabies vaccine at monthly intervals and four rounds of SMC with SP+AQ at monthly intervals. In 2018 and 2019, these children received one dose of a control vaccine (Hepatitis A) and four rounds of SMC at monthly intervals.

Extension study:

All children in the SMC group received a single dose of a Tetanus Toxoid (in Burkina Faso) or Tetanus/Diphtheria toxoids (in Mali) vaccine in June 2020, and four rounds of SMC at monthly intervals between July and October 2020.

Children in the SMC group exactly five years of age, or below, on 1st June 2021 received an additional dose of Tetanus toxoid vaccine in June 2021 (in both Countries), and either four rounds of SMC (in Mali) or five rounds of SMC (in Burkina Faso) at monthly intervals between July and October 2021. This change in Burkina Faso for 2021 resulted from the National Malaria Control Programme choosing to deploy 5 courses of SMC in Houndé district.

### Group 2 – RTSS/ AS01E arm – 'RTS,S alone'

Original Trial:

In 2017, children in the RTS,S/AS01E group received three doses of RTSS/AS01E vaccine and four rounds of placebo-SMC at monthly intervals. In 2018 and 2019, children received one dose of RTS,S/AS01E vaccine in June (prior to the malaria transmission season) and four rounds of placebo-SMC at monthly intervals.

Extension study:

All children in the RTS,S alone group received a single dose of RTS,S/AS01E in June 2020 (prior to the malaria transmission season), and four courses of placebo SMC at monthly intervals between July and October 2020.

Children in the RTS,S alone group exactly five years of age, or below, on 1st June 2021 received an additional dose of RTS,S/AS01E vaccine in June 2021 (prior to the malaria transmission season), and four courses of placebo SMC (in Mali) or five courses of placebo SMC (in Burkina Faso) at monthly intervals between July and October 2021.

### Group 3 – RTS,S/AS01+SMC arm – 'Combined arm'

Original trial:

In 2017, children in the combined group were given three doses of RTS,S/AS01E vaccine and four rounds of SMC with SP+AQ at monthly intervals. In 2018 and 2019, children received one dose of RTS,S/AS01E vaccine in June (prior to the malaria transmission season) and four rounds of SMC with SP+AQ at monthly intervals.

Extension study:

All children in the Combined group received a single dose of RTS,S/AS01E in June 2020 (prior to the malaria transmission season), and four courses of SMC at monthly intervals between July and October 2020.

Children in the Combined group exactly five years of age, or below, on 1st June 2021 received an additional dose of RTS,S/AS01E vaccine in June 2021 (prior to the malaria transmission season), and either four rounds of SMC (in Mali) or five rounds of SMC (in Burkina Faso) at monthly intervals between July and October 2021.

The study groups, and abbreviated names used for ease of reference, are shown in the table below. The interventions given during the initial three-year trial, and the two-year extension are shown in separate sections.

[figure not shown]
**Table 1.** Study Interventions

| Group                    |  |  |  |
|---------------------------------|--|--|--|
|                                 | 1) SMC
'SMC alone'  | 2) RTS,S/AS01E
'RTS,S alone' | 3) RTS,S/AS01E +SMC
'Combined group' |
| Initial three-year trial |  |  |  |
| April/May – June/July 2017      | Rabies vaccine x 3   | RTS,S/AS01 E x 3                        | RTS,S/AS01 E x 3                                |
| July/Aug – Oct/Nov 2017         | SMC x 4  | SMC placebo x 4                                    | SMC x 4  |
| June 2018                       | Hep A vaccine x 1  | RTS,S/AS01 E x 1                        | RTS,S/AS01 E x 1                                |
| July-Oct 2018                   | SMC x 4  | SMC placebo x 4                                    | SMC x 4  |
| June 2019                       | Hep A vaccine x 1  | RTS,S/AS01 E x 1                        | RTS,S/AS01 E x 1                                |
| July-Oct 2019                   | SMC x 4  | SMC placebo x 4                                    | SMC x 4  |
| Two-year Extension Study |  |  |  |
| June 2020                       | Tetanus (BF) or
Tetanus/Diphtheria
toxoids (Mali) x 1 # | RTS,S/AS01 E x 1                        | RTS,S/AS01 E x 1                                |
| July-Oct 2020                   | SMC x 4  | SMC placebo x 4                                    | SMC x 4  |
| June 2021*                      | Tetanus toxoid x 1 #  | RTS,S/AS01 E x 1                        | RTS,S/AS01 E x 1                                |
| July-Nov 2021* \$    | SMC x 4
(Mali)  | SMC placebo x 4
(Mali)                          | SMC x 4
(Mali)  |
|                                 | SMC x 5
(Burkina Faso)  | SMC placebo x 5
(Burkina Faso)                  | SMC x 5
(Burkina Faso)                                  |

\* Only children aged 5 years or below on June 1st 2021 were eligible to receive study intervention in 2021.

# In 2020, due to difficulties shipping tetanus toxoid vaccine from India as a result of the COVID-19 outbreak, children in group 1 in Burkina Faso received tetanus toxoid vaccine from stocks held by Burkina Faso's national infant immunization programme. Children in group 1 in Mali received tetanus/diphtheria toxoids vaccine from stock held by Mali's national infant immunization programme. In 2021, children in both countries received tetanus toxoid vaccine supplied by the Serum Institute of India.

\$ In Burkina Faso, in 2021, the National Malaria Control Programme began to deliver 5 monthly courses of SMC in the study area. To ensure that our intervention reflected the current standard of care, the study team also administered 5 SMC courses in 2021.

**Figure 1.** Schematic of Key Study Activities in the Initial Trial Period, and in the Two-Year Extension

Only children aged below 5 years on June 1st 2021 were eligible to receive study intervention in 2021.

**Precise timing of interventions during the original trial, and the extension study***Administration of RTS,S/AS01E or control vaccine:*

## Original trial:

Administration of the first dose of study vaccines began in late April 2017 in all three study groups, and was completed by mid-May. The third dose was given between late June and early July 2017. In 2018 and 2019, single doses of RTS,S/AS01E or control vaccine were given in the first two weeks of June.

## Extension study:

In June 2020, vaccinations were given to all children in the study. In June 2021, vaccinations were given to all children exactly five years of age, or below, on 1st June 2021.

*Administration of SMC or placebo SMC:*

## Original trial:

In 2017, administration of the first SMC course began in late July and was completed by the end of the first week of August, with subsequent cycles on a monthly basis thereafter. In 2018 and 2019, administration of the first SMC course began in the second week of July, and was completed by mid-July. Subsequent courses were delivered monthly thereafter. Earlier delivery in 2018 and 2019 was necessary to ensure that drug administration was completed before SMC delivery through the national malaria control programme took place.

## Extension study:

In 2020, SMC was administered to all children, as four monthly courses, starting in July. In 2021, all children exactly five years of age, or below, on 1st June 2021 received SMC, starting in July 2021. In Mali, children received four courses of SMC in 2021. In Burkina Faso, children received 5 cycles in 2021, because the national programme decided to deliver five cycles of SMC in Houndé district.

## **Study population in the original trial**

Children of either sex were eligible for inclusion in the trial, provided that they were 5-17 months of age on the scheduled date of first vaccination in April 2017, they were living permanently in the study area, and the consent of a parent or legally acceptable representative was obtained.

Children with a history of an adverse reaction to SP or AQ, known to have a serious underlying illness including known HIV infection not well controlled by treatment, having severe malnutrition (z scores < 3 SD) or known to have previously received a malaria vaccine were excluded from the trial.

Children known to have received SMC during the year prior to enrolment (either through the previous study in these districts (AZ-SMC, [NCT02211729](https://clinicaltrials.gov/ct2/show/NCT02211729)), or from the national programme) were not excluded from this study.

The list of eligible children in each country was sorted by location (village), age in months, gender and prior receipt of SMC, before assigning randomisation codes in permuted blocks of 9, to give an implicit stratification on these factors.

Children who were randomized but who did not receive the first dose of study vaccines in 2017 were deemed to have withdrawn consent and were not followed up further. Consequently, analyses from baseline of all the children who remained under observation constitute a modified ITT population, rather than the full ITT population. Analyses during specific years of the study, or during the extension study period only, reflect the children remaining in follow-up at that point, rather than analysis by intention to treat.

## **Inclusion criteria for the Extension study**

[figure not shown]
In order to be eligible to participate in the extension study, a child must have been enrolled in the initial phase of the trial of seasonal vaccination with the RTS,S/AS01E vaccine and their parents or guardian must have provided consent for their inclusion in the extension study.

As described above, children above the age of 5 years on 1st June 2021 were no longer eligible to receive either of the interventions, but were followed until the end of the extension study on safety grounds and to begin longer-term monitoring for any increased risk of malaria in the period after the interventions were no longer given.

## **Exclusion criteria for the extension study**

Any child who met any of the following criteria was excluded from participation in the extension study:

- a. The child had had an allergic reaction to the study drugs or vaccines.
- b. The child had febrile convulsions on more than one occasion following vaccination.
- c. The child had a serious underlying illness, such as severe malnutrition (weight for age or mid arm circumference Z scores < 3 SD), which in view of the investigators might impair the response to vaccination.
- d. The child had been enrolled in another malaria vaccine or other experimental malaria intervention study.

**Figure 2.** CONSORT chart for the initial phase of the trial and the extension study

\* Some of the numbers in the figure above are provisional, and may change for the final analysis once all data cleaning is complete.

### **Illustrative sample size calculations for the extension study period**

In Burkina Faso and Mali, 2777 and 3143 children respectively, received the first dose of study vaccine and were enrolled in the initial trial. In Burkina Faso 2410 out of 2510 children remaining in follow-up at the end of the three-year trial consented to join the extension study. In Mali, 2624 out of 2680 children remaining in follow-up after three years consented to join the extension phase of the trial (Figure 2).

**Non-inferiority Comparison:** SMC for four months of the year has an efficacy, assuming receipt of all four monthly cycles, of about 85% during this 4-month period. If, without intervention, the peak four months of malaria incidence would account for 60% of annual cases (with the other 40% falling during the other months) this equates to an efficacy over 12 months of at least 50%. The non-inferiority margin is the largest reduction in this efficacy that policy makers would be likely to accept if RTS,S/AS01 was to replace SMC, taking into account of the potential advantages of RTS,S over SMC in terms of ease of delivery and the potential to sustain a high level of coverage. A reduction in annual efficacy from 50% to 40% was considered the largest difference that would be likely to be acceptable. This lower efficacy would translate to a 20% greater incidence in the RTS,S/AS01-alone arm compared to the SMC-alone arm.

The study has greater than 90% power to exclude, at the 2.5% significance level, a relative difference in the incidence of clinical malaria of 20% over the five year study period between the RTS,S/AS01 and the SMC alone groups if these two interventions were equally effective. To determine the level of confidence with which this margin can be excluded, we will also calculate two sided 90% and 99% confidence intervals. With the anticipated incidence rates, there is adequate power to reject a smaller margin. However, 20% was considered the largest difference that would be considered unimportant.

**Superiority Comparison:** The primary end-point for the trial is the incidence of clinical episodes of malaria. Based on incidence during the first three years of the trial (305 cases per 1000 child-years in the SMC alone group), and taking account of the fact that the incidence of clinical episodes of malaria in children still protected by study interventions may decline with age, we assume that the incidence of malaria will be at least 200 cases per 1000 child-years at risk over the entire study period. Based on this assumption, the study will have 90% power to detect a 12.0% or greater relative difference (absolute difference: 24 cases per 1000 child-years) between the RTS,S/AS01E + SMC combined group and the RTS,S/AS01E alone or SMC alone groups, through a standard superiority comparison during the five years of the trial. In the first three years of the trial, the incidence was about 60% lower in the combined group (rather than 12%), so the extension study should have very high power for the superiority comparisons.

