### 3. OBJECTIVES AND PURPOSE

#### **Primary objective:**

The primary objectives of the extension study are to determine, among children aged three or four years of age who have previously received RTS,S/AS01E alone, SMC alone or both interventions since the age of 5-17 months:

- a. Whether the combination of seasonal vaccination with the malaria vaccine RTS,S/AS01E with SMC with SP+AQ is superior to the administration of either intervention given alone in preventing clinical attacks of malaria, defined as an episode of illness characterised by fever (temperature  $\geq 37.5^{\circ}\text{C}$ ), or a history of fever within the past 48 hours, that is severe enough to require treatment at a health centre or by a community health worker and which is accompanied by a positive blood film with a parasite density of 5,000 parasites per  $\mu\text{l}$  or more.
- b. Whether seasonal vaccination with RTS,S/AS01E alone is non-inferior to SMC alone in preventing clinical attacks of malaria, defined as above.

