## **10.2 Sample size and analysis of the primary efficacy endpoint**

At a survey conducted in April 2019, 5363 of the 5887 (91%) children enrolled in the first phase of the trial were contactable, an annual loss of about 5%. Assuming that this rate of attrition continues for a further year and that a similar proportion of families do not consent for their child to join the extension study, it is likely that approximately 4,800 children will enter the extension study.

The primary analyses will cover the entire study period, ie. the initial three years of the study and the two year extension period. The entire study period is defined as the time from enrolment in June 2017 until the end of the study year in which the child reaches five years of age and is no longer eligible for SMC, i.e. between 5 and 20 months of age (depending upon the exact age at first vaccination) and 60-71 months of age (depending upon the timing of the child's fifth birthday in relation to the SMC schedule). On the basis of date of enrolment, the exit dates above, and losses to follow-up as described above, we estimate that there will be approximately 20,625 person-years of follow-up during the entire study period: 6875 person-years per study group (i.e. an average of 3.5 person-years per child originally recruited).

The primary end-point for the trial is the incidence of clinical episodes of malaria. Based on data from the first two years of the ongoing study, we assume that the incidence of malaria will be 200 cases per 1000 children per year over the entire study period. Based on this assumption, the study will have 90% power to detect a 12.0% or greater relative difference (absolute difference: 24 cases per 1000 child-years) between the RTS,S/AS01E + SMC and the RTS,S/AS01E alone or SMC alone groups, through a standard superiority comparison.

The study will also have 90% power using a two sided 95% confidence interval to exclude a 17.5% relative difference (absolute difference: 35 cases per 1000 child-years) in incidence of clinical malaria between children in the RTS,S/AS01E alone or SMC alone group, using a non-inferiority design, over the entire study period. To determine the level of confidence with which this margin can be excluded, we will also calculate two sided 90% and 99% confidence intervals.

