### **Analyses in individual years**

There will be approximately 4,100 child-years of observation in the year following the third booster; 1367 child-years in each study group. Assuming the incidence of clinical episodes of malaria remains at about 200 episodes per 1,000 children per year during this period, the study will have 90% power, through a standard superiority comparison, to detect a 25.9% or greater

relative difference (absolute difference: 52 cases per 1000 child-years) between the Combined RTS,S/AS01E + SMC group and the RTS,S/AS01E alone or SMC alone group.

A similar analysis will be undertaken for the final year of the study following administration of a fourth booster dose of the RTS,S/AS01E or comparator vaccine but study power will be reduced because slightly more than half of the children enrolled (3860/5920) will not be eligible for SMC in 2021-22, and thus will not contribute further events nor person-time at risk to the study period.

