**Strategy to address multiplicity**

Hypothesis testing for analyses of the primary outcome will follow the closed testing procedure, whereby there is initially a test of the null hypothesis that the incidence in the three groups is the same. If this is rejected at the 5% level, pairwise comparisons will be done also using a 5% significance level. Pairwise comparisons can be considered statistically significant only if the overall null hypothesis is rejected. P-values and 95% confidence intervals will be presented.

For the non-inferiority comparison of the primary outcome described above, we will calculate two-sided 95% confidence intervals, equivalent to the use of a one-sided significance level of 2.5%, as is recommended (4). To illustrate the level of confidence with which non-inferiority can be declared, we will plot the point estimate for the hazard ratio with two-sided 90, 95 and 99% confidence intervals, and the non-inferiority margin (a hazard ratio of 1.2, which would reflect 20% higher incidence of clinical malaria in children in the RTS,S/AS01E alone group, relative to the SMC alone group).

For secondary outcomes, we will present 95% confidence intervals, without adjustment for multiplicity, stating that no adjustment was made.

For safety outcomes, we will present p-values and 95% confidence intervals, without adjustment for multiplicity.

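### The 90% power for superiority is for one pairwise test before the SAP's three-group gate; with the gate it is about 88% for one comparison and about 83% for both

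*Combined protocol and SAP*

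**What the plan says.** In the SAP, the superiority paragraph under the illustrative sample size calculations starts from an incidence floor: "we assume that the incidence of malaria will be at least 200 cases per 1000 child-years at risk over the entire study period". It then states that "the study will have 90% power to detect a 12.0% or greater relative difference", the contrast being the combined group against the RTS,S "alone or SMC alone groups, through a standard superiority comparison during the five years of the trial". Protocol section 10.2 gives the same figure and supplies the follow-up: "6875 person-years per study group (i.e. an average of 3.5 person-years per child originally recruited".

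For year 4, the SAP section on individual years says "There will be approximately 4,100 child-years of observation in the year following the third booster; 1367 child-years in each study group" and claims 90% power "through a standard superiority comparison, to detect a 25.9% or greater" relative difference. Protocol 10.2 repeats this.

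The SAP's multiplicity section sets the decision rule. A test that the three groups have the same incidence comes first, at 5%. Pairwise tests follow, also at 5%, and "Pairwise comparisons can be considered statistically significant only if the overall null hypothesis is rejected". The SAP plans hypothesis tests for the whole intervention period and for study years 4 and 5, so the rule covers both power statements.

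Protocol section 3, primary objective a, asks whether the combination "is superior to the administration of either intervention given alone in preventing clinical attacks of malaria". The SAP's extension objective is narrower: whether further vaccine doses add protection when given with SMC.

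**The concern.** The power statements describe one test and the SAP will apply another. A pairwise test that would succeed alone can be blocked by the three-group test, so the probability of a declarable result is below the stated 90%. If objective a is taken to require superiority over each single intervention, two correlated tests must both succeed, and the probability falls further. A reader who takes 90% as the chance of reaching the superiority conclusion at a 12.0% difference would put the risk of missing it at 10%. Under the both-arms reading it is about 17%.

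**Working it through.** **Inputs.** Rate in each single arm: 200 per 1000 (SAP, superiority paragraph). Child-years per group: 6,875 for the whole period (protocol 10.2) and 1,367 for year 4 (SAP, individual years). Global and pairwise tests at 5% (SAP, multiplicity section). The superiority text does not state sidedness, so two-sided is assumed. The form of the three-group test is not given, so a 2-df homogeneity test is assumed. Variance is plain Poisson.

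**Step 1: reproduce the stated figure.** For one ungated comparison, power = Φ(d / √((λ0 + λ1)/PY) − 1.96).

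- Whole period: d = 0.200 − 0.176 = 0.024; standard error = √(0.376/6875) = 0.00740; ratio 3.245; power = Φ(1.285) = 90.1%.
- Year 4: d = 0.200 − 0.1482 = 0.0518; standard error = √(0.3482/1367) = 0.01596; ratio 3.246; power = Φ(1.286) = 90.1%.

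A one-sided 5% test would give 94.5%, which does not match. The stated 90% is therefore one two-sided 5% comparison with no gate.

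**Step 2: apply the SAP's rule.** Poisson counts in three arms, 1,000,000 replicates; the 2-df test at 5%, then pairwise tests at two-sided 5%. Both single arms are at 200 per 1000 and the combined arm is lower by the stated difference.

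| | Whole period, 12.0% | Year 4, 25.9% |
|---|---|---|
| One comparison, no gate | 90% | 90% |
| Three-group test rejects | 93% | 93% |
| One comparison, with gate | 88% | 88% |
| Both comparisons, no gate | 83.4% | 83.5% |
| Both comparisons, with gate | 83.0% | 83.0% |

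A bivariate normal check on the ungated both-comparisons figure (correlation 0.47 and 0.43 through the shared combined arm) gives 83.2% and 82.9%. The gate costs about 2 points for one comparison and about 0.5 point once both are required. Nearly all of the fall to 83% comes from requiring both.

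**Step 3: difference detectable with 90% power, both comparisons plus gate.** About 13.1% for the whole period (0.131 × 200 = 26 per 1000) and 28.2% for year 4 (0.282 × 200 = 56 per 1000). Simulated power at these values is about 90%.

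**Step 4: sensitivity.**

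- *RTS,S alone, one comparison (combined against SMC).* Gated power is about 88% if RTS,S alone equals the combined arm and about 83% if it lies midway between SMC alone and the combined arm, in both periods.
- *RTS,S alone 10% worse than SMC alone (220 per 1000).* Gated power against both arms is about 90% in both periods, so the shortfall disappears.
- *Higher rate.* With both single arms at 240 per 1000, gated power against both is about 90% in both periods.
- *Larger effect.* At a 60% reduction, power against both with the gate is about 100% in both periods. With an assumed threefold variance inflation it is still 99.7% in year 4.

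**The case against.** The strongest reply is that nothing is miscalculated. The text names a standard superiority comparison against one arm or the other, under a heading that calls the calculations illustrative, and the figures reproduce. That stands: a reader might infer that the 90% is an arithmetic error, and it is not.

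A reader might also infer that the trial's power simply is 83%. The documents do not support that. No section makes success depend on winning both comparisons. The SAP's extension objective concerns added benefit over SMC, and SMC alone is the reference group. On that reading, with equal single arms, gated power is about 88%.

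The whole-period shortfall also treats a floor as the expected rate. The SAP says at least 200 and reports 305 per 1000 in the SMC arm over the first three years, which belong to the whole period. Of 20,625 child-years, 4,100 fall in year 4. If year 5 is assumed to add 1,400 to 1,700, the first three years hold 14,825 to 15,125, or 72 to 73%. At 305 per 1000 they alone contribute 219 to 224 per 1000 to the average. An overall rate near 240, where gated power against both returns to 90%, is therefore plausible if RTS,S alone runs at a similar rate. This argument does not reach year 4.

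Finally, the planned analysis is a country-stratified Cox model with robust standard errors. The documents give no overdispersion value, so the Poisson figures here are approximations, as are the plan's own.

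What remains is that no power statement mentions the gate, although the gate decides what may be called significant.

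**Conclusion.** The point holds as a mismatch between the power statements and the decision rule. The 90% is right for one ungated pairwise test. Under the SAP's rule it becomes about 88% for one comparison, or about 83% if superiority over both single arms is required, at 12.0% overall and 25.9% in year 4. These figures rest on equal single arms at 200 per 1000, Poisson variance and a 2-df global test. The 83% also rests on reading objective a as requiring both wins. The shortfall exists only near the minimum detectable difference. At the reduction of about 60% that the SAP reports from the first three years, it has no practical effect on the superiority conclusion. Importance is low.

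**What to change.** In the SAP's superiority paragraph, its section on individual years, and protocol 10.2:

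- Label the 90% as power for one pairwise comparison before the three-group test.
- Add the gated figures: about 88% for one comparison and about 83% for both. Alternatively, give the differences detectable with 90% power on both, about 13.1% (26 per 1000) for the whole period and 28.2% (56 per 1000) for year 4.
- State that these figures assume equal single arms, 200 per 1000 and no overdispersion, and that power is near 100% at the reduction of about 60% already seen.

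The cost is two or three sentences in each document. The testing procedure, the number of children and the analyses stay as they are.
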